There are two main types of respiratory training: inspiratory training, also called inspiratory muscle strength training (IMST), and expiratory training, also called expiratory muscle strength training (EMST). In this application, we propose a novel, proof-of-concept study to test whether the addition of either type of respiratory training to the standard of care voice therapy (voice exercises) enhances respiratory and voice outcomes. This study will permit, for the first time, the comparison between inspiratory and expiratory training. The theoretical framework is: inspiratory training strengthens the inspiratory muscles and thus increases both vital capacity and the ability to counteract passive recoil of the lungs, improving

the quantity of and control over the airflow available to drive the vocal folds. Expiratory training strengthens the expiratory muscles to expand the expiratory reserve volume and provide more airflow for voicing. Using pulmonary function tests and respiratory pressure measures, combined with voice assessments, we will specifically evaluate our hypotheses and determine the independent effects of inspiratory training and expiratory training on respiratory function and voice production. We will also evaluate the interaction between the type of respiratory training and a patient's baseline respiratory function. This will provide mechanistic information to guide the future selection of the type of respiratory training to augment voice therapy, to promote an impairment-specific intervention paradigm.

Forty-eight participants diagnosed with presbyphonia will be included in the study and will be stratified and blocked-randomized into one of the three intervention groups (two experimental groups and one control group), using a 3-parallel arm design: 1) inspiratory training (IMST) (experimental group), 2) expiratory training (EMST) (experimental group), or 3) voice exercises (VFE) (control group), delivered four times during a 60-minute therapy session. Monitored home practice will consist of 10 minutes of twice daily exercise for the duration of therapy. Participants from all three groups will carry on with their standard of care voice therapy with a certified SLP.

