Specific Aim 1: To measure the effects of respiratory training on respiratory and voice outcomes in patients with presbyphonia. Hypothesis 1: The respiratory training groups (inspiratory and/or expiratory) will demonstrate greater improvement in respiratory outcomes, measured through pulmonary function tests and respiratory pressure measures, compared with the voice exercises-only group. Hypothesis 2: The respiratory training groups (inspiratory and/or expiratory) will demonstrate greater improvement in voice-related outcomes than the voice exercises-only group.

Secondary Aim 1: To assess the reliability of the ratings for subjective outcomes (videostroboscopy ratings and perceptual judgements of voice quality). Hypothesis 1: Intra-judge reliability will be of at least 80%. Hypothesis 2: Inter-judge reliability will be of at least 70%.

Specific Aim 2: To determine how baseline measures of respiratory function influence the effects of respiratory training (respiratory and voice outcomes). Hypothesis 1: inspiratory training will have maximal effect on patients with decreased maximum inspiratory pressure (MIP). Hypothesis 2: Expiratory will have maximal effect on patients with decreased maximum expiratory pressure (MEP).

This is an initial feasibility and mechanistic study that has the potential to reveal that respiratory training can significantly improve outcomes from voice therapy by acting in synergy with voice exercises. Currently,

much time is spent in voice therapy on subthreshold 'breathing exercises' that lack evidence. This project will provide guidance for evidence-based and theory driven approaches to leverage respiratory function to improve voice therapy. Conversely, negative findings from this study would indicate that respiratory function is ineffective and not a viable target for therapy in this patient population.

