The effects of respiratory training on voice outcomes have never been studied on patients with presbyphonia despite the declines in respiratory function that occur with aging. Both inspiratory and expiratory pressures can be reduced in elderly patients, yielding different impairment profiles (10). Since inspiratory muscles are crucial for increasing inspiratory lung volume and for counteracting expiratory pressures to enhance airflow control during sustained speech, increasing their strength appears to be a viable target to improve the loudness and duration of speech (29). However, some individuals may have difficulty generating sufficient subglottal pressure despite initiating phonation at high lung volume because of reduced ribcage compliance and lung recoil forces(11, 12). For those patients, early activation of the expiratory muscles might be the most effective strategy to increase vocal efficiency, by compressing the chest wall to a smaller volume and generating the required airway pressure for speech production (19, 30). These patients may optimally benefit from expiratory training. Although some patients may benefit from both inspiratory and expiratory training, there is a need to assess the individual effects of both interventions prior to testing their combined effect in a future study to understand the mechanism of action and optimize the use of therapy time. Thus, we propose to study how differences in patients' baseline respiratory function impacts intervention response, specifically which patients benefit from inspiratory training and which patients benefit from expiratory training.

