The contributions of this study will be to: 1) assess the relevance of respiratory training when treating patients with presbyphonia; 2) determine the mechanistic respiratory and voice effects of respiratory training for patients with presbyphonia, and 3) identify profiles of patients likely to benefit from each type of respiratory training. These contributions would be significant as they would begin to provide speech language pathologists (SLPs) with evidence pertaining to rigorous respiratory training for presbyphonic patients. After the study results are validated, SLPs will be able to determine, based on their clinical assessment, which patients should undergo respiratory training and which modality would be maximally beneficial, inspiratory or expiratory training, or both. This would improve the outcomes and efficiency of voice therapy. If respiratory training results in meaningful voice quality changes for patients with presbyphonia, it may also indicate a novel modality for use with other hypofunctional voice disorders (e.g. adductor paralysis).

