Inspiratory and expiratory training have never been conducted on patients with presbyphonia. To determine the adequate intensity and duration of treatment, we reviewed the literature of respiratory training interventions with patients of similar age groups. We decided on a threshold of 75% of MIP and MEP because 1) this value was widely used across studies, resulted in significant improvements in respiratory outcomes, and has been shown to be safe(16, 32-34); 2) maximal improvements in muscle strength have been reported to occur with a loading at 70-90% of the maximal strength(14). The regimen of 5 sets of 5 breaths was also widely used across studies, along with a threshold at 75% of MIP/MEP, and resulted in improved respiratory outcomes. We chose to have the participants practice their exercises every

day of the week because in our opinion it is the best way to create a habit and therefore enhance compliance to treatment.

Voice Exercises [Standard of care intervention]: Participants will be instructed to follow the four steps of the VFE protocol, developed by Stemple (35) and commonly used by SLPs with patients with presbyphonia: (a) sustain the vowel /i/ on the musical note F (above middle C for women; below middle C for men) for as long as possible. (b) Glide from the lowest note to the highest note on the word "knoll". (c) Glide from the highest note to the lowest note of the word "knoll". (d) Sustain the notes C-D-E-F-G (starting from middle C for women and an octave below middle C for men) on the word "oll", for as long as possible. Each note will be repeated until the participant finds the right placement (forward-focused voice), as judged by the SLP. Humming exercises will be used to facilitate placement. Daily practices, 2x/day, will consist of two repetitions of the VFE protocol for the IMST and EMST groups and four repetitions of the VFE protocol for the VFE group. Recordings of the therapy sessions will be provided to facilitate home practice.

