12.0 Data Management

Data Analysis Plan

Demographic characteristics will be compared across the 3 intervention groups, using a RxC contingency table method for categorical variables (gender, smoking history, voice use, racial and ethnic category) and a one-way ANOVA for continuous variables (age, weight, height). Baseline characteristics will be compared across the 3 intervention groups using a Kruskal-Wallis one-way analysis of variance by ranks for ordinal data (GFI, RSI, and VHI scores), a RxC contingency table for categorical variables (glottal gap shape, free edge contour, vertical level, phase closure) and a one-way ANOVA for continuous variables. Aim 1: To assess the effects of respiratory training on voice and respiratory outcomes in patients with presbyphonia. Data will be analyzed on an intention-to-treat basis using multifactor repeated measures generalized linear regression. Distributional assessment will be made for each outcome to confirm optimal distributional assignment and potential need for outcome transformation (i.e. log link). In the model, the repeated factor is time, which has two levels (pre- or post-intervention) and the independent factor is the intervention, which has three levels (IMST, EMST, VFE). In the case of a significant between-subjects effect, multiple comparison tests will be conducted to determine which groups differ. The post-hoc analysis will be done using Tukey's honestly significant difference (offering protection against type I error without being too conservative). Spearman and Person correlations will be calculated to establish inter and intrarater reliability. Aim 2: To identify profiles of presbyphonic patients that would benefit the most from respiratory training. Logistic regression will be conducted to predict which patients improved following inspiratory training and which patients improved following expiratory training, based on their baseline clinical characteristics. Two outcome variables will be indicative of meaningful clinical improvement: 1) MPT (to measure function), and 2) GFI (to measure patient perception of function). Meaningful clinical improvement will be defined by an increase of at least 4 seconds in MPT or a decrease of at least 4 points in GFI score. Participants will be dichotomized as having meaningful clinical improvement, or not, based on these outcomes. Predictors will include MIP, MEP, maximum SPL, breaths per minute, FVC, FEV1, and P_s. These measures were chosen because they are directly influenced by the integrity of the respiratory system.

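### The Aim 2 analysis states no VFE comparison, arm term or arm-by-baseline term, so it cannot test the effect-modification hypotheses set for Aim 2 in Section 1.0

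*Combined protocol and SAP*

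**What the plan says.** **The aims.** Section 1.0 says the study will "evaluate the interaction between the type of respiratory training and" a patient's baseline respiratory function. Specific Aim 2 is "To determine how baseline measures of respiratory function influence the effects of respiratory training (respiratory and voice outcomes"). Its two hypotheses are "inspiratory training will have maximal effect on patients with decreased maximum inspiratory pressure (MIP") and "Expiratory will have maximal effect on patients with decreased maximum expiratory pressure (MEP"). Section 2.0 (Background) says the study will show "specifically which patients benefit from inspiratory training and which patients benefit from expiratory training", and lists as a contribution that it will "identify profiles of patients likely to benefit from each type of respiratory training". Only the Aim 2 hypotheses name MIP and MEP; the other statements speak of baseline respiratory function or patient profiles.

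**The analysis.** Section 12.0 (Data Analysis Plan, Aim 2) gives one method: "Logistic regression will be conducted to predict which patients improved following inspiratory training and which patients improved following expiratory training". Improvement is dichotomised at a 4-second gain in MPT or a 4-point fall in GFI. Seven baseline measures are listed as predictors: MIP, MEP, maximum SPL, breaths per minute, FVC, FEV1 and subglottal pressure. VFE patients are not mentioned, nor is any arm term or product of arm and baseline.

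**Elsewhere.** The Aim 1 model has time and a three-level intervention factor but no baseline MIP or MEP term. The Sample Size Justification only repeats the responder thresholds for Aim 2. Section 10.0 stratifies on MIP/MEP status, which balances the arms but does not supply the missing model terms.

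**The concern.** The aims concern effect modification: whether the benefit of a training over its comparator changes with baseline MIP or MEP. The stated analysis answers a different question, namely who got better among those trained.

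Section 10.0 puts all three groups on the VFE protocol. A patient who improves after IMST may have improved because of VFE, and a baseline value that predicts this improvement may do so equally in the VFE arm. Without that arm in the model, prognosis and effect modification cannot be separated.

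What is at stake is the purpose of Aim 2. A prognostic marker could be carried forward as the profile of who should receive IMST or EMST, and so misdirect the next study and the choice between the two trainings.

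**Working it through.** **1. The plan's own figure.** Section 12.0 uses d=0.90, alpha 0.1 and 80% power. Two-sided, n = 2(1.645+0.842)²/0.90² = 2×6.18/0.81 = 15.3, which rounds up to 16 per group. The stated 15 gives power Φ(0.90/√(2/15) − 1.645) = Φ(0.82) = 79%. The figure is reproduced closely, but it sizes a difference between groups. The plan gives no figure for the Aim 2 interaction.

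**2. What the stated model estimates.** Write expected improvement in arm *a* as α_a + β_a×MIP. The effect of IMST over VFE at a given MIP is (α_IMST − α_VFE) + (β_IMST − β_VFE)×MIP. The first Aim 2 hypothesis is about β_IMST − β_VFE, and the training-type interaction is about β_IMST − β_EMST. A model within IMST estimates β_IMST alone. A model pooling the trained arms without an arm-by-MIP term estimates an average of β_IMST and β_EMST. Neither yields the required difference.

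More patients would not help. In a simulation with 100 per arm, a log-odds slope of 0.7 or 1.1 per SD in every arm and no interaction, the within-IMST fit flagged the baseline value in 96% and 100% of runs. The arm-by-baseline test flagged it in 9–12%.

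**3. Size at the planned numbers.** Assumptions, none given in the documents:
- MIP has the same correlation r with improvement in every arm, lower MIP going with more improvement.
- About half of patients respond.
- MIP is the only predictor.
- The criterion is a likelihood-ratio p<0.10, borrowed from the Sample Size Justification because Aim 2 has no decision rule.

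There is no effect modification, so every flag is a false lead.
- One trained arm, n=15, at r = 0, 0.1, 0.2, 0.3, 0.4, 0.5: about 13%, 16%, 19%, 27%, 38%, 52%.
- Both trained arms pooled, n=30: about 11–13% at r=0, then 38–40%, 57–58% and 76% at r = 0.3, 0.4, 0.5.

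The r=0 rate is the inflated size of the small-sample test. Only the excess over it is due to prognosis. Wald tests at n=15 give lower rates: 7%, 8% and 10% at r = 0, 0.1, 0.2, and 16%, 23–24% and 34% at r = 0.3, 0.4, 0.5.

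**4. The matching test.** A linear model over three arms (intercept, two arm terms, baseline outcome, MIP, two arm-by-MIP terms: seven parameters) rejects in about 10% of runs for IMST-versus-VFE and 9–11% for IMST-versus-EMST, when slopes are equal.

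**5. Unequal VFE repetitions.** Section 3.0 prescribes "two repetitions of the VFE protocol for the IMST and EMST groups and four repetitions of the VFE protocol for the VFE group". If the MIP slope of the response to VFE were 0.4 at four repetitions and 0.2 at two (assumed), IMST-versus-VFE would differ by 0.2 with no modification by training, and would be flagged in about 14–15% of runs. IMST-versus-EMST has equal repetitions and keeps expectation zero.

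**6. Precision.** The two halves of a normal baseline differ in mean by 2√(2/π) = 1.60 SD. An effect differing by 0.90 SD between halves is therefore a slope difference of 0.90/1.60 = 0.56 SD per SD. At 15 per arm, power for that is about 41% and the 90% interval is about ±0.7; 80% power needs about 42 per arm.

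**7. Several contrasts.** Four slope contrasts on two outcomes make eight. With r=0.4 and no effect modification, at least one reaches p<0.10 in about half of runs (46–52%).

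**The case against.** The strongest reply has four parts.

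*The text may not be exhaustive.* The predictor list is worded so that other terms could be added, and Section 12.0 restates Aim 2 as identifying patient profiles. A reader might infer that the plan rules out an interaction. It does not; it states none. But every item listed is a baseline measure, and no other section supplies an arm term, so the gap stands.

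*The size depends on assumed correlations.* This is correct. At r of 0.1 to 0.2 the single-arm rates (16–19%) are little above the 13% null rate, and with a Wald test there is no excess over 10%. The simulated sign also favours the plan's hypotheses; an opposite sign would not lend them support. The mismatch between aim and model does not depend on r.

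*The remedy has its own false leads.* This is also correct. The 10% is per contrast, about half of studies would show at least one contrast at p<0.10, and VFE contrasts are affected by the unequal repetitions. These limits must be stated, but they do not make a within-arm model answer the question.

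*This is a pilot.* Section 1.0 calls it an initial feasibility and mechanistic study, and Section 2.0 makes clinical use conditional on validation. That limits the harm to a wrong lead for later work.

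Two further inferences go too far. One is that seven predictors will be fitted separately to about 15 patients and the estimates will fail to exist: the plan does not say that the arms are fitted separately or that all seven enter together. The other is that logistic regression or the responder thresholds are themselves wrong: the gap can be closed with both retained.

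**Conclusion.** The point holds. Section 1.0 sets effect-modification hypotheses for Aim 2, and the analysis stated in Section 12.0 cannot test them, whether the trained arms are modelled separately or pooled. That conclusion is structural and rests on the text alone.

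The numerical risk is conditional. If MIP is moderately prognostic in all arms (r of 0.3 to 0.5), false attribution is roughly two to four times the null rate in a single arm and three to seven times when pooled. If it is weakly prognostic, the excess in a single arm is small. The documents do not support saying that Aim 2 will give a wrong answer, or that Aim 1 is affected. This should be fixed before the data are analysed.

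**What to change.** In Section 12.0, Aim 2:

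- Fit the model to all three arms with arm, baseline MIP and arm × MIP, and a second model with MEP in place of MIP, for MPT and for GFI.
- Report with confidence intervals the IMST-versus-VFE difference in MIP slope, the EMST-versus-VFE difference in MEP slope, and the IMST-versus-EMST differences in both slopes.
- As a minimum, add these terms to the planned logistic model. Modelling continuous change in MPT and GFI, adjusted for the baseline outcome, is preferable: at 15 per arm the logistic likelihood-ratio interaction test has size about 15% against 10% for the linear model, and power about 35% against 41%. The 4-second and 4-point responder results can stay.
- Label the analysis exploratory. Say that several contrasts on two outcomes are examined, so some will reach p<0.10 by chance.
- State that the VFE contrasts compare training plus two VFE repetitions with four.
- Label the other listed predictors prognostic unless an arm interaction is fitted for them.

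If the interaction is not to be analysed, reword the aims in Section 1.0 and the matching statements in Section 2.0 to within-arm prediction of response.

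The cost is analysis wording only: Section 10.0 (Data Collection) says the same data serve both aims, and the VFE arm is already randomised and measured. The price is wide intervals and low power, which the report should state.

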Patient self-assessments: Patients are asked to complete the 1) Voice Handicap Index (VHI): a questionnaire that evaluates the degree of handicap experienced by the patient in relation to their voice use(41); 2) the GFI(42): a validated disease-specific impairment instrument conceived to assess symptoms related to glottal insufficiency; 3) the RSI(43), a validated self-administered questionnaire to assess symptoms related to LPR; and 4) the Communicative Participation Item Bank (CPIB) general short form(44). Patients are also asked to rate their perceived phonatory effort (PPE) on a direct magnitude estimation scale(45) following the speaking and voicing tasks recorded with the CSL.

Aerodynamic measures: The Phonatory Aerodynamic System (PAS) is used to measure 1) mean glottal airflow rate: estimated from sustained phonation of a vowel(36); 2) average subglottal air pressure (P_s): measured during the production of a voiceless plosive consonant (/p/) at normal pitch and loudness, an accepted indirect and non-invasive measurement method for P_s (46); and 3) laryngeal resistance: calculated by dividing subglottal pressure by mean glottal airflow.

Phonation duration (MPT): The maximum phonation duration of the vowel /a/ is measured via CSL.

Respiratory measures (respiratory measures will be recorded solely as part of the study).

Spirometry: Spirometry will be used to measure 1) forced vital capacity (FVC), 2) forced expiratory volume in one second (FEV1), and calculate the 3) FEV1/FVC ratio. The predicted values (%) of these three measures will also be reported. The patient will be asked to take a full inspiration, blow out the air forcefully and then exhale slowly to residual volume in the spirometer. The task is repeated at least three times, until the two best measurements differ by no more than 0.15.

Muscle pressure measures: 1) MIP: measured at functional residual capacity, is an indicator of inspiratory muscle strength. Patients will be instructed to exhale fully and then inhale with maximal effort with lips sealed to the pressure meter for at least 2 seconds. 2) MEP: measured at full lung capacity, is an indicator of expiratory muscle strength. Participants will be instructed to take a full breath and then exhale with maximal force with lips sealed to the pressure meter for at least 2 seconds.

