
Sample Size Justification

We considered maximum phonation time (MPT) as the primary outcome measure for sample size calculation. This measure was chosen because 1) low MPT is a hallmark of patients with presbyphonia, and 2) MPT is directly affected by both the laryngeal and respiratory systems. To estimate the expected effect size between VFE and the I+IVFE and E+VFE groups, we considered MPT values from groups of an

elderly population with different glottal closure and spirometry profiles (49). Considering that a combined intervention (inspiratory or expiratory training combined with voice therapy) would address both laryngeal and respiratory deficits, and that a voice therapy-only intervention would directly address only the laryngeal deficits, we compared MPT between the no-deficit group (complete glottal closure and normal spirometry) and the respiratory-deficit group (complete glottal closure and altered spirometry)(49). Based on these values and the pooled standard deviations, the expected difference between our control and experimental groups would represent a large effect size. As for the withinsubjects effect, a study by Nam et al.(50) found a 33% increase in MPT following a respiratory training intervention program in young adult singers. This corresponds to a very large within-subjects effect size with values of d exceeding 1.2. For Aim 2, we will assess improvement in 2 ways: function (a MPT increase of 4 seconds, which has been associated with a positive perceived effect following voice therapy in older adults(51)) and patient perception of function (a Glottal Function Index (GFI) score decrease of 4 points). An increase of 4 seconds in MPT and a decrease of 4 points on the GFI instrument both correspond to medium-large effect sizes considering the reported standard deviations of these measures in older subjects and in patients with glottal insufficiency (5.1 and 4.5, respectively) (42, 52). Based on the reported studies, the expected effect size for within-subjects and between-subjects differences was set at d=0.90. To have an 80% power to detect an effect size of d=0.90 with an alpha of 0.1 (since this is a pilot study), 15 participants are needed in each group. To account for loss to follow-up (estimated 10% dropouts rate), up to 16 participants will be recruited for each group, 48 patients total.

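### Aim 2 names respiratory and voice outcomes, but no planned model tests whether baseline MIP or MEP modifies the respiratory effect of training

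*Combined protocol and SAP*

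**What the plan says.** **The aim.** Section 1.0 (Objectives / Specific Aims) gives Specific Aim 2 as: "To determine how baseline measures of respiratory function influence the effects of respiratory training (respiratory and voice outcomes". Its first hypothesis is that "inspiratory training will have maximal effect on patients with decreased maximum inspiratory pressure (MIP"; the second says the same of expiratory training and MEP. Earlier in that section the sponsor undertakes to examine how the type of training interacts with respiratory function at baseline.

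**The analysis.** Section 12.0 (Data Management, Data Analysis Plan) restates the aim as: "To identify profiles of presbyphonic patients that would benefit the most from respiratory training". The method is logistic regression, with the outcome described thus: "Two outcome variables will be indicative of meaningful clinical improvement: 1) MPT (to measure function), and 2) GFI (to measure patient perception of function". The cut-offs follow, the second of them applying to the GFI: "Meaningful clinical improvement will be defined by an increase of at least 4 seconds in MPT or a decrease of at least 4 points in". On the other side of the model, "Predictors will include MIP, MEP, maximum SPL, breaths per minute, FVC, FEV1, and P_s". The Sample Size Justification names the same two measures for Aim 2.

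**Aim 1.** The model in section 12.0 has time (two levels) and intervention (three levels). It contains no baseline respiratory term and no stratum term.

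**Data.** Section 10.0 schedules spirometry at baseline and after the fourth session, and muscle pressure at baseline and before and after every session. It says the same data serve both aims.

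**The concern.** The aim covers two outcome domains and its analysis covers one. The respiratory part disappears between section 1.0 and section 12.0 without explanation.

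This matters because the study describes itself as mechanistic. Its framework is a chain: training strengthens respiratory muscle, stronger muscle improves the airflow available for voicing, and voice improves. Baseline MIP and MEP bear most directly on the first link, and section 10.0 treats stratification on them as essential to the design. If the MPT/GFI model finds no relation with baseline MIP or MEP, the plan offers no way to tell whether weak patients failed to strengthen or strengthened without a voice gain. Those two results point to different next studies, and section 2.0 intends the profiles to guide the choice between inspiratory and expiratory training.

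**Working it through.** **1. The plan's own figure.** The Sample Size Justification gives 15 per group for d = 0.90, alpha 0.1 and 80% power. Taken as two-sided, n = 2 × ((1.645 + 0.842) / 0.90)² = 15.27, which rounds up to 16; power at 15 per group is 79.4%. The figure reproduces to within rounding. It comes from a comparison of two means and says nothing about effect modification, so it does not settle this point.

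**2. Planned models by domain and question.**

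| Outcome domain | Does the arm matter? | Does the effect depend on baseline respiratory function? |
|---|---|---|
| Voice | Aim 1, time and intervention | Aim 2, logistic regression on MPT/GFI improvement |
| Respiratory (MIP, MEP, FVC, FEV1) | Aim 1, time and intervention | none |

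One cell of four is empty, and section 1.0 assigns that cell to Aim 2.

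**3. Could MPT fill the cell?** Section 4.0 lists it before the separate heading for respiratory measures: "Phonation duration (MPT): The maximum phonation duration of the vowel /a/ is measured via CSL". Aim 1, Hypothesis 1, takes respiratory outcomes to be pulmonary function tests and respiratory pressures. MPT is neither.

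**4. Could Aim 1 fill it?** Its time and intervention factors give the average respiratory change in each arm. Without a baseline-by-arm term they cannot show whether that change differs between patients with low and with preserved MIP or MEP.

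**5. What would fill it.** For MIP:

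final MIP = b0 + b1·IMST + b2·EMST + b3·MIP0 + b4·(IMST × MIP0) + b5·(EMST × MIP0) + error

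Here MIP0 is baseline MIP and VFE is the reference arm. Hypothesis 1, read for a respiratory outcome, predicts b4 below zero. For MEP the same model uses baseline MEP, and the coefficient of interest is b5. VFE has to stay in the model: low baseline values tend to rise on retest without training. That tendency sits in b3, so b4 and b5 measure what training adds.

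**6. Precision.** Six coefficients and 3 × 15 = 45 participants leave 39 residual degrees of freedom. With equal baseline SD in the two arms compared, SE(b4) = (residual SD / baseline SD) × √(2/14) = 0.378 × ratio. The 95% half-width is 2.02 × 0.378 × ratio = 0.76 × ratio. The documents give neither SD, so the ratio is an assumption: at 0.5 the half-width is 0.38, and at 1.0 it is 0.76. A slope difference of −0.38 would mean that a participant 10 cmH2O weaker at baseline gains 3.8 cmH2O more from training, relative to VFE. Only modification of at least about that size could be told apart from zero.

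**The case against.** The best defence is that section 12.0 sets out to define meaningful clinical improvement and to find who benefits. For that question, a patient who gains inspiratory strength but has neither a qualifying MPT rise nor a qualifying GFI fall has had no clinical voice benefit, and the rule scores that patient as intended. This stands. A reader might infer that the rule misclassifies participants whose strength rises. The documents do not support that: a strength gain neither causes nor prevents a score of not improved, which follows only when both thresholds are missed.

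Two further points soften the concern. The Sample Size Justification says "MPT is directly affected by both the laryngeal and respiratory systems", so MPT carries some respiratory information. It remains a partial proxy and does not measure respiratory strength. And Aim 1 will show whether IMST and EMST raise MIP and MEP overall, so a null Aim 2 would be ambiguous only about patients with low baseline values.

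The Aim 2 hypotheses also speak of a maximal effect without naming an outcome. Reading them as predictions about MIP and MEP change is an inference from the aim statement above them, which does name both domains.

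None of this supplies the missing model.

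**Conclusion.** The point holds as a mismatch of scope. Section 1.0 promises an analysis of how baseline respiratory function influences the respiratory effect of training, and section 12.0 contains none. It should be put right before analysis. It does not touch the Aim 1 comparison of arms, the sample size or the validity of the MPT/GFI rule. A reader might conclude that respiratory outcomes go unanalysed in the trial; Aim 1 covers them by arm, and only their dependence on baseline is missing.

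The size is one empty cell of four. No bias or loss of power in an existing analysis is claimed. The conclusion rests on a comparison of the text and needs no outside figure; only the precision estimate uses an assumed SD ratio.

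**What to change.** In section 12.0, keep the MPT/GFI logistic regression and label it the voice part of Aim 2. Add a respiratory part:

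- Regress final MIP on arm, baseline MIP and arm-by-baseline MIP, using all three arms; do the same for MEP.
- Report the IMST-versus-VFE slope difference for MIP and the EMST-versus-VFE slope difference for MEP as estimates with confidence intervals. No new responder cut-off is needed.
- State which reading counts as final, since pressures are taken both before and after session four.
- FVC and FEV1 can be treated the same way as supportive outcomes.

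The cost is a paragraph of SAP text and two regressions on data already scheduled, with no extra visit, test or participant. The downside is imprecision: with about 15 per arm (16 × 0.9 = 14.4 after the assumed dropout), the intervals will be wide and a null result should not be read as absence of modification.

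If the sponsor intends a voice-only Aim 2, the alternative is to narrow both the aim statement and the interaction objective in section 1.0, and to draw no conclusion about respiratory effect modification.
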